As presented in Figure 1, the duration of the main study for each patient will be up to 6 weeks, which includes two active 1-week sessions, as well as time for screening and scheduling gap of up to 4 weeks between the sessions. There will be up to 5 visits, including screening, study training prior to the first study week, one outpatient (CDT Research House) experimental session and one visit following conclusion of the control week. The outpatient experimental session will last approximately 40 hours. For subjects participating in the substudy, an additional 5 day study period will occur any time after randomization..

E. Inclusion Criteria

1. ≥ 21 and < 65 years old.
2. Clinical diagnosis of type 1 diabetes mellitus. For an individual to be enrolled at least one criterion from each list must be met.
 - Criteria for documented hyperglycemia (at least 1 must be met):
 - i. Fasting glucose ≥ 126 mg/dL – confirmed
 - ii. Two-hour OGTT glucose ≥ 200 mg/dL – confirmed
 - iii. HbA1c $\geq 6.5\%$ documented – confirmed
 - iv. Random glucose ≥ 200 mg/dL with symptoms
 - v. No data at diagnosis is available but the participant has a convincing history of hyperglycemia consistent with diabetes

- Criteria for requiring insulin at diagnosis (1 must be met):
 - i. Participant required insulin at diagnosis and continually thereafter
 - ii. Participant did not start insulin at diagnosis but upon investigator review likely needed insulin (significant hyperglycemia that did not respond to oral agents) and did require insulin eventually and used continually
 - iii. Participant did not start insulin at diagnosis but continued to be hyperglycemic, had positive islet cell antibodies – consistent with latent autoimmune diabetes in adults (LADA) and did require insulin eventually and used continually
- 3. Use of an insulin pump to treat his/her diabetes for at least 1 year.
- 4. Familiarity with a bolus calculator with the current insulin pump with pre-defined parameters for carbohydrate [CHO] ratio, insulin sensitivity factor [ISF], target glucose and active insulin.
- 5. HbA1c <9% as measured with DCA2000 or equivalent device.
- 6. Not currently known to be pregnant, breast feeding, or intending to become pregnant (females).
- 7. Demonstration of proper mental status and cognition for the study.
- 8. Willingness to avoid consumption of acetaminophen-containing products 24 hours prior to and during CGM use.

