If a subject meets all the study criteria, he/she will be enrolled in the trial. The total amount of blood to be withdrawn during the screening visit is ~6 cc. The screening visit will last approximately 2 hours. If the subject cannot schedule the session within 8 weeks of screening, screening labs, vital signs, and recent medical illness/medications will be re-evaluated. The study physician will have the discretion to repeat any test as needed.

All subjects will also be given written instructions to avoid acetaminophen prior to their study intervention or to reschedule their study intervention if they require acetaminophen as there is potential for interference with glucose oxidase systems for measuring glucose such as the Dexcom CGM. These instructions will also advise the subject to contact the study team in the event of a febrile illness within 24 hours of the study intervention, so that the study week can be rescheduled. All subjects will be given written instructions to bring all of their current medications and pump supplies with them for use during the experimental session.

2. Activities Performed During the Study Weeks

Outpatient Study Training Visit including use of Continuous Glucose Monitor (CGM)

1. An outpatient visit will be scheduled at the beginning of the first study week (experimental or control depending on the randomization). For subjects who are prior Dexcom CGM users, this visit may occur over the phone.
2. The subject's insulin pump, CGM receivers, and the subject's personal glucometer will be set using atomic clocks as a reference.
3. Quality control testing will be performed on the subject's personal glucometer as recommended in the manufacturer guidelines. If available, a concentration in the hypoglycemic range will be tested. A tested glucometer will not be used in a study if it does not read within the target range at each concentration per manufacturer labeling. session
4. Female subjects of childbearing potential will perform a urine pregnancy test. If positive, the subject will discontinue study participation. The subject will be asked to seek confirmation of the test and the appropriate medical care. No payment will be given if the subject is cancelled due to pregnancy.
5. Subjects who are proficient CGM users prior to the Study Training visit may elect to initiate the CGM sensor at home rather at the training visit.

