11. The study subject will be instructed to follow a similar hypoglycemia and hyperglycemia safety protocol as the experimental session (the Home Glycemic Safety Protocol, Appendix A-6).
12. In addition to device-required calibrations, an additional calibration will be performed prior to the evening meal +/- 30 minutes to minimize the likelihood that a calibration is requested close to the time of the study meal. The CGM will be calibrated per manufacturer's guidelines with the study glucometer.
13. The subject will have access to ad lib glucose-free beverages.
14. The study subject will continue with the data collection process as described during Days 1-5.
15. Study personnel will be in frequent contact with the study subject during this phase of the study.
16. The study subject will be asked to confirm the time and content of meals and snacks when they occur. They will also notify study personnel of SMBG values.
17. Study subject will be asked to be at home with comparable physical activity level as the experimental session.
18. The study subject will return to the office on approximately Day 7. Data will be downloaded from all devices.

Pilot Session:

Up to two subjects will participate in a pilot experimental session. These subjects will follow the same procedures as Outpatient Study Visit for Continuous Glucose Monitor (CGM) Training. Data Collection Period (Days 1-5) does not need to be collected. Procedures for Pilot Session will be the same as and are described in "Procedures for the Experimental Session" *except for the procedures detailed below*. A pilot subject may also participate in 40-hour trial.

- Closed loop (AAA) will be initiated at 19:00 and proceed through Day 2 at 17:00 (22 hours). Components of the AAA system will be active at the same corresponding times within that timeframe:
 - SSM and BRM will be active throughout the study period (19:00 Day 1 through 17:00 Day 2).
 - AM will be active 19:00 Day 1 through 23:00 Day 1 and 7:00 Day 2 through 17:00 Day 2.
 - The same procedures will be followed as described in "Procedures for the Experimental Session".
- Discharge will begin at 17:00. The DiAs will stop AAA control. The system components (CGM sensors, study pump) will be removed.
 - The subject will resume his/her normal home pump therapy.
 - A fingerstick value will be obtained.
 - The subject will be discharged by approximately 18:00 if the following 3 conditions below are met:
 - the fingerstick value is 80-249 mg/dL

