 - the glucose trend is stable
 - Insulin on Board is appropriate as determined by the MD
 - If the subject's glucose is out of the specified parameters, the Hypoglycemia or Hyperglycemia Safety Protocol will be followed until the subject is in the specified

- range.
- Study staff will request that the subject remains at the Research House until approximately 18:00. Subjects will be offered dinner.
 - Study staff will contact the subject within 24-48 hours after discharge.

Procedures Related to the Substudy:

Five to eight subjects may enroll in the substudy at any time after randomization.

1. Subjects will wear the Accu-Chek Spirit Combo pump during the entire substudy (5 days). Specific training will be given for the Accu-Chek Spirit Combo including the Accu-Chek Aviva Combo device which subjects will use during the day. This training will occur as a separate outpatient visit or while admitted to the CDT Research House during the primary study based on subject convenience. A study pump used for training purposes may be utilized. A qualified staff member will conduct the training and in particular discuss differences from their home pump in important aspects such as calculation of insulin on board.
2. The Accu-Chek Spirit pump will be programmed with the study subject's usual basal rates from 07:00 to 22:00. DiAs will be turned on in open loop between 20:00 - 22:00 and therefore the study pump will be programmed for a basal rate of 0 from the initiation of DiAs control until 07:00. This will allow for DiAs to operate. If there is any unforeseen delay of more than 15min in initiating DiAs in open loop, a basal rate will be entered into the Accu-Chek Spirit Pump until connection can be established.
3. After 07:00, the study subject may leave the research study house and participate in their usual activities (work, home) during the day. Activities should be similar to the 5 day period #1 of CGM-augmented insulin pump therapy during the main study. Subjects will be requested to remain within the greater Charlottesville area (~approximately 25 miles radius) during this time. The subjects will have unlimited access to study MD and qualified medical study personnel by phone, email, text or in person if needed to address any concerns during the day with use of the pump or other clinical concerns.
4. Subjects will be asked to return to the research study house by approximately 18:00.
5. The study pump and CGM will be downloaded.

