In the unlikely event of a disruption in 911 phone service, the Charlottesville-UVA-Albemarle Emergency Communications Center can be reached via their non-emergency number [contact]. This number feeds into their main call area where 911 dispatchers are available 24/7.

J. ENDPOINTS

This study is an early feasibility study that will test the efficacy of DiAs - a *smart-phone-based system* compared to CGM-enhanced insulin pump treatment in an outpatient setting. Specifically, the main study will have randomized cross-over design with each patient participating in two study weeks: 1) experimental involving 5 days of data collection followed by 2 days of AAA control using insulin pump and available CGM (however, treatment based on CGM will be discouraged) and 2) Control week involving 5 days of data collection followed by 2 structured days of study at home. This series of sessions will provide data for the regulatory approval of the AAA system and for its deployment in a longer-term trial of AAA at home. In addition, the data will be used to estimate the effect size of the AAA vs. CGM-enhanced insulin pump treatment in an outpatient setting.

The *basic unit for most analyses is the glucose trace of an individual*, i.e. a time-stamped series of CGM data recorded for each person. Summary characteristics and group-level analyses are derived after the individual traces are processed to produce meaningful individual markers of average glycemia and glucose variation. The following primary endpoints will be assessed:

- Risk for hypoglycemia as measured by the Low BG Index associated with exercise (SA1);
- Time spent within 70-180 mg/dl during the day (SA2);
- Risk for hypoglycemia overnight and time spent within the target range of 80-140 mg/dl overnight (SA3).

In addition, the following secondary endpoints will be assessed:

- Extent postprandial glucose excursions during the day;
- Overall number and extent of hypoglycemic episodes;
- System reliability, including failure rates of system components, frequency analysis of lost or inaccurate CGM records, percent time of active control, and inter-device connections between DiAs and the CGM and between DiAs and the insulin pump;
- System functionality, including the DiAs GUI in terms of patient comfort with operating the system, and
- The DiAs remote monitoring by medical personnel/technicians to confirm appropriate functioning outside of the hospital setting.

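### The 5-night closed-loop substudy may fall before or between the two cross-over weeks, so up to 8 of 36 subjects could bring extra, non-randomised exposure into a primary comparison

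*Combined protocol and SAP*

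**What the plan says.** Two places set the timing. Section I.G.5, Procedures Related to the Substudy, says "Five to eight subjects may enroll in the substudy at any time after randomization". Section I.D (Study Duration) says that "an additional 5 day study period will occur any time after randomization", and allows "time for screening and scheduling gap of up to 4 weeks between the sessions".

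The order of the main weeks is fixed before the first begins. Section I.G.2 reads "An outpatient visit will be scheduled at the beginning of the first study week (experimental or control depending on the randomization". Section I.J describes the design: "the main study will have randomized cross-over design with each patient participating in two study weeks".

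In the substudy, SSM+BRM run from 23:00 to 07:00 on five consecutive nights. Item 3 of the substudy procedures adds: "Activities should be similar to the 5 day period #1 of CGM-augmented insulin pump therapy during the main study". SA4 compares the substudy with CGM-augmented pump therapy alone and does not say which nights supply that comparison.

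Section I.L plans a repeated measures ANOVA with contrasts. It names no sequence, period, carry-over or prior-substudy term. Section VII says that each of the three control modules can be adapted with a subject's prior data. It does not say whether substudy data may be used for this.

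**The concern.** In a cross-over, each subject's two sessions should differ only in the treatment and the randomised order. A substudy taken before or between them adds a further block of the tested intervention. Neither its timing nor its recipients are randomised. Control may then follow extra nights on the system, or the experimental session may start with modules already adapted on substudy data. SA3 is most directly exposed, because SSM and BRM are the modules that run overnight in the experimental session.

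There is also a conflict within the text. If the substudy comes before week 1, the first 5-day period has not taken place and activities cannot be matched to it.

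**Working it through.** **Which sessions can follow the substudy.** Setting the timing rule beside the fixed order gives:

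| Substudy entry | Main sessions that follow it |
|---|---|
| Before week 1 | Both, in either order |
| Between weeks, experimental first | Control only |
| Between weeks, control first | Experimental only |
| After both weeks | None |

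The text permits all four rows. It sets no washout, no minimum gap and no requirement to finish the main study first.

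**Number of subjects.** Inputs are 5 to 8 substudy subjects (I.G.5) and 36 completers (I.C). If all enter early, 8/36 = 22.2% or 5/36 = 13.9%. If all enter after both weeks, the figure is 0.

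**Amount of exposure.** Substudy: 5 nights x 8 h = 40 h. Main experimental session: 19:00 on Day 5 to 07:00 on Day 7 = 36 h, covering 2 nights. The ratio is 2.5 by nights and about 1.1 by hours (40/36).

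**The plan's own power.** I.C states 97% for SA1, a similar value for SA3 and 85% for SA2, at N = 36 and alpha 0.01. Section I.K gives an effect size of 0.3-0.5 without defining it. For a paired comparison, power = Φ(dz·√n − z). Two-sided alpha is assumed, so z = 2.576.

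- 0.3-0.5 read as dz: Φ(0.3 x 6 − 2.576) = 22% to Φ(0.5 x 6 − 2.576) = 66%.
- 0.3 read as Cohen's f with an assumed within-subject correlation of 0.5: dz = 0.6, and Φ(0.6 x 6 − 2.576) = 84.7%.

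The 85% can be reached under one unstated reading, so the stated powers are neither confirmed nor refuted. I take them as given and solve back: dz = (2.576 + 1.036)/6 = 0.602 for 85%, and (2.576 + 1.881)/6 = 0.743 for 97%.

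**Illustration of dilution.** The carry-over sizes are assumed; the documents give none. If the treatment difference shrinks by a fraction c in all 8 subjects, with the SD unchanged, the mean effect is multiplied by 1 − (8/36)c:

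| c | Factor | Power from 85% (SA2) | Power from 97% (SA1; SA3 called similar) |
|---|---|---|---|
| 0.25 | 0.944 | 80% | 95% |
| 0.50 | 0.889 | 74% | 92% |
| 1.00 | 0.778 | 59% | 81% |

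This is the unfavourable end, because all eight must shift the same way. Suppose all eight entered between the weeks, with 1:1 allocation (ratio not stated) and entry unrelated to order. The chance that control came second for every one of them is then 0.5^8 = 0.4%.

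**Leaving early entrants out.** N = 36 − 8 = 28 or 36 − 5 = 31. Power falls from 85% to Φ(0.602·√28 − 2.576) = 73% or to 78%, and from 97% to 91% or 94%.

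**With the substudy last.** 0 of 36 carry substudy exposure into a main session, and N stays at 36.

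**The case against.** The strongest reply is that the design already accepts prior exposure. Everyone randomised to the experimental week first meets control after 36 hours of AAA. A reader might infer that the substudy spoils an otherwise unexposed control, but this cross-over never had one. What stands is narrower: the existing exposure follows the randomised order, and substudy exposure does not.

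There is also separation. Five days of data collection at home precede each session, and subjects return to their home pump when the substudy ends. This makes lasting carry-over less likely, though the plan does not present it as a washout, and it does not settle whether substudy data may be used to adapt the modules.

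Other stronger readings are not supported:

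- *Practice would inflate SA3.* SSM and BRM are automated and run while the subject sleeps. The user-operated Advisory Module is not among the modules switched on in the substudy, and all subjects are trained on DiAs for the experimental session.
- *The substudy can precede its own comparator.* The first 5-day period is named only for matching activities. It is not stated to be the SA4 comparator.
- *Subjects select themselves.* Section I.G.3 calls them selected, without saying how.
- *No analysis could deal with it.* Timing can be recorded, and a handful of subjects can be left out of a sensitivity analysis.

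Some text hints at later entry. Section I.G.3 mentions the substudy when describing the end of the 5-day collection period, and pump training may take place during the main-study admission. Neither is a rule. I could not see Figure 1. Whether pilot subjects who later join the 40-hour trial count among the 36 is a separate matter.

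**Conclusion.** The point holds as a gap in the scheduling rule. Up to 8 of 36 subjects (22%) could carry extra, non-randomised closed-loop exposure into a primary session. The true number may be anything from 0 to 8, depending on when they enter. This is a possible bias, not a demonstrated one. Its direction may differ between subjects, and entry before week 1 precedes both sessions and may partly cancel. The power figures rest on assumed carry-over, a two-sided test and the plan's unverified powers, so they show scale and do not predict a loss.

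One element needs no assumption about carry-over: entry before week 1 is allowed, yet it makes the activity-matching instruction impossible to follow. SA4 is exploratory with no significant results expected, so little is gained by leaving the primary comparisons open to this.

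**What to change.** In Section I.D and in the substudy procedures of I.G.5, replace the open timing clause with *after completing both main-study sessions*. Name the nights that supply the SA4 comparison, for example those of the first 5-day period, which will by then have been collected.

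If earlier entry is kept, record when each subject took the substudy relative to both sessions, and prespecify in Section I.L a sensitivity analysis of SA1-SA3 excluding subjects who did the substudy before either main session. Also reconcile the activity-matching instruction with entry before week 1.

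The preferred change costs wording and scheduling only: the substudy runs slightly later and may draw fewer volunteers for an exploratory aim. The fallback keeps the flexibility, but its sensitivity analysis could rest on as few as 28 subjects.

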6. Dinner will occur between approximately 18:00-19:00.
7. Hypoglycemic treatments can occur at any time per the subject's request. In addition, the Home Glycemic Safety Protocol will be followed by the study subject.
8. The subject will be started on DiAs in open loop mode between 20:00 – 22:00. When DiAs is operating, the Accu-Chek Aviva Combo Device is not paired to the pump and is unable to communicate with the pump. The subject will use the One Touch Ultra 2 or Aviva Combo glucometer for fingersticks while the DiAs is operating.
9. Subject may administer correction boluses per their usual regimen at any time prior to closed loop control initiation which is approximately 23:00.
10. The system will turn on SSM+BRM at 23:00 to 07:00.
11. At approximately 23:00, lights will be turned out, and the subject will be encouraged to sleep.

12. The staff will be checking the readings of the secondary CGM receiver at 03:00 AM and 05:00 AM during the night and will monitor remotely the subject.
13. CGM will be calibrated in the same manner as described in Procedures Related to the Experimental Session.
14. The subject will be awakened shortly before 7:00 AM and allowed time for routine hygiene.
15. A fingerstick value will be obtained upon waking while the subject is still fasting.
16. At 7:00 AM, DiAs will be stopped and the subject will resume CGM-augmented insulin pump therapy. These same procedures will be repeated for 5 consecutive nights. Subjects will be able to leave the CDT each morning if SMBG is 80-249 mg/dL, and glucose trend is stable. A meal will be offered.

Procedures Related to Discharge (Day 6 of substudy)

1. The subject will be awakened shortly before 7:00 AM and allowed time for routine hygiene.
2. A fingerstick value will be obtained upon waking while the subject is still fasting.
3. At 7:00 AM, DiAs will be stopped and the system components (CGM, pump) will be removed.
4. The subject will resume his/her normal home pump therapy.
5. A fingerstick value will be obtained.
6. The subject will be discharged by approximately 9:00 AM if the following 3 conditions below are met:
 - a. the fingerstick value is 80-249 mg/dL
 - b. the glucose trend is stable
 - c. Insulin on Board is appropriate as determined by the MD
7. If the subject's glucose is out of the specified parameters, the Hypoglycemia or Hyperglycemia Safety Protocol will be followed until the subject is in the specified range.
8. The subject will be offered a meal prior to discharge.

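### Substudy item 2 ends the pump's own basal at a fixed 22:00 but also sets it to zero when DiAs starts, at any time from 20:00 to 22:00; the two instructions conflict for up to 2 hours a night

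*Combined protocol and SAP*

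**What the plan says.** All the relevant text is in section I.G, Procedures Related to the Substudy.

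- Item 2, first setting: the study pump carries the subject's "usual basal rates from 07:00 to 22:00".
- Item 2, start window: "DiAs will be turned on in open loop between 20:00 - 22:00". Item 8 repeats it: "The subject will be started on DiAs in open loop mode between 20:00 – 22:00".
- Item 2, second setting: "the study pump will be programmed for a basal rate of 0 from the initiation of DiAs control until 07:00". The reason given is "This will allow for DiAs to operate".
- Item 2, delay rule: for "any unforeseen delay of more than 15min in initiating DiAs in open loop, a basal rate will be entered into the Accu-Chek Spirit Pump", and that rate stays until the connection is made.
- Item 10: the safety supervision and basal rate modules (SSM and BRM) run from 23:00 to 07:00.
- Item 16: the procedure is repeated on five consecutive nights. The section's opening line gives five to eight subjects.

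**The concern.** The first setting ends at a clock time. The second begins at an event whose time varies by two hours. Item 2 does not say how the two are matched, who changes the pump, or when. Staff who follow the first setting and staff who follow the second would have the pump doing different things on any night when DiAs starts before 22:00.

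What is at stake is mainly safety. This is a contradictory insulin-delivery instruction for an investigational system, and in the disputed hours the automated hypoglycaemia protection is not yet on. Section H also places the hours before 23:00 under the home glycaemia protocol rather than the protocols used when SSM and BRM are active. The statistical stake is smaller: insulin given, or not given, late in the evening might still act after 23:00, on the DiAs nights only, in a comparison of five to eight subjects.

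**Working it through.** The plan states no overlap or gap figure to reproduce, so the check is clock arithmetic on the inputs listed above. Let S be the DiAs start time, between 20:00 and 22:00.

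**1. Length of the conflict.** From S to 22:00 the first setting calls for usual basal and the second for zero. Conflict = 22:00 − S.

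| DiAs start S | Conflict that night |
|---|---|
| 20:00 | 2 h |
| 21:00 | 1 h |
| 22:00 | 0 h |

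Per subject, the maximum is 5 nights × 2 h = 10 h, reached only if DiAs starts at 20:00 every night.

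**2. When the conflict becomes double delivery.** Two conditions are needed: the 22:00 profile is left running after S, and DiAs delivers basal in open loop. The documents imply the second without stating it: zero pump basal is there so that DiAs can operate, and the DiAs training text in section H has DiAs loaded with the subject's pump settings and the basal rates confirmed. If both conditions hold, double delivery lasts 22:00 − S, at most 2 h. If the pump is set to zero at S, it lasts 0 h. The documents give no basal rates. Purely as an assumption, 0.5 to 2 U/h would make a 2 h overlap 2 × 0.5 = 1 U to 2 × 2 = 4 U in a night.

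**3. When a gap without basal could arise.**

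- Profile to 22:00, zero from actual S, and S no later than 22:00: gap = 0.
- DiAs late, after 22:00: the profile has ended. If the delay counts from 22:00, the rule limits the gap to about 15 min plus the time to enter a rate.
- Zero set in advance for an expected start E, and DiAs starts later at S: the gap would be S − E. The rule limits it to about 15 min plus entry time if the delay counts from E, but not if it counts from the end of the window.

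The third case shows why the missing reference time matters. It also bears on what the rule presupposes. If zero is set only at actual start, a delay inside the window leaves usual basal running and no rate needs entering. The rule therefore has work to do only after 22:00 or where zero was set beforehand.

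**4. Position relative to SA4.** The conflict always ends by 22:00. SSM and BRM start at 23:00, so the separation is 23:00 − 22:00 = 1 h.

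**The case against.** The strongest reply is that the second setting qualifies the first. It is presented as a consequence of the DiAs start, so a sensible reader sets pump basal to zero when DiAs begins, and no overlap occurs. Subjects are asked to be back at the research house by about 18:00 and the home glycaemia protocol applies until 23:00, so an error might be noticed. The substudy is exploratory, and section J expects no significant result from it.

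Much of this stands. Double delivery is conditional, and following the second setting prevents it. But that reading leaves the 22:00 end time without a function for every earlier start, and the text does not say which instruction prevails. The mitigations may soften the consequences; they do not settle what the pump should be programmed to do.

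Three stronger readings are tempting and are not supported:

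- *Two hours with no basal.* Zero is tied to DiAs initiation, not to 20:00, and the delay rule sits in the same item. A 2 h gap needs zero set at 20:00, a 22:00 start, and a wait that nobody counts as an unforeseen delay. The text does not prescribe this.
- *A wrong dose every night in every subject.* The conflict is 0 h at a 22:00 start and shrinks as the start moves later. Whether DiAs would account for the pump's own basal cannot be judged, because the DiAs manual (Appendix A-7) is not in the document.
- *A biased SA4 effect size.* The disputed hours lie before the period in which SSM and BRM act. Carry-over is plausible but not shown.

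**Conclusion.** The contradiction is real and nothing else in the document resolves it. It should be corrected before the instruction is used, because it concerns insulin delivery at a time when SSM is inactive. Its size is 0 to 2 h per night and at most 10 h per subject. That figure rests only on the stated clock times and the five nights. Double basal is a possible result that depends on the two conditions in step 2, one of them inferred. The delay rule is incomplete because it has no reference time in a two-hour window and is silent on overlap. For SA4 the most that can be said is that carry-over is possible and unquantified. SA1 to SA3, the sample size and the power statements are unaffected.

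**What to change.** The sponsor and study physician should reconcile the fixed 22:00 end of the pump's basal profile with the variable DiAs start in items 2 and 8, so that the text gives one instruction for every permitted start time. They should state the time from which the 15-minute delay is counted and have the actual changeover time recorded each night, so that any carry-over into the SA4 period can be examined. The choice of schedule is theirs.

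The cost is a one-paragraph amendment and one line on a nightly checklist. No extra staff time of note is needed, since DiAs is started each evening anyway. Because the change bears on subject safety, section VIII would route it through the IRB and the appropriate regulatory bodies before it is implemented.
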